12.1.4. Follow-up of Adverse Events

All reported AEs should be followed until resolution or until the subject's participation in the study ends. Subjects with the following types of events should be followed by the Investigator until the event is determined to be resolved, irreversible, chronic, stable, the subject withdraws consent, or no further information can be reasonably obtained.

- On-going SAEs
- On-going ESIs (excluding medication errors not resulting in AEs)
- Early termination and withdrawal from the study due to study drug related AEs

In addition, on a case by case basis, Santen (or designee) may request follow up beyond the scheduled exit visit.

The follow-up information on an individual SAE, AE, or ESI will be entered into the eCRF prior to database lock. If the information requested by Santen is not part of the eCRF, or when database lock has already been completed, the site's response to follow-up requests should be emailed, faxed or reported to Santen Pharmacovigilance: [contact] or [contact] (fax for the Philippines sites) or [contact] (fax for the US sites).

12.1.5. Manual Back-Up Reporting Procedures

This study is utilizing an electronic data capture (EDC) system for data collection. In the event that the EDC system is unavailable for electronic reporting, the manual back-up reporting procedures below should be followed.

- Complete an AE and SAE form manually
- Attach a cover sheet with your contact information, including site number.
- Email (preferred) or Fax the cover sheet and the AE and SAE form to Santen Pharmacovigilance at [contact] or [contact] (for the Philippines sites) or [contact] (for the US sites).

When the EDC system becomes available, update the EDC system with all previously reported information.

12.2. Safety Parameters

The safety assessments will include AEs, slit lamp biomicroscopy, indirect ophthalmoscopy, BCVA, IOP, fundus photography, fluorescein angiography, serum chemistry, hematology, urinalysis, vital signs, physical examination, EKG, and pregnancy.

12.2.1. Physical Examination

A full body systematic physical examination will be conducted by the Clinical Investigator or an external internist.

12.2.2. Electrocardiogram (EKG)

The Clinical Investigator will review the EKG report for abnormalities.

12.2.3. Vital Signs

Blood pressure and heart rate will be measured using an automated or manual blood pressure monitor. Systolic and diastolic blood pressures will be recorded in millimeters of mercury (mmHg), and heart rate will be recorded in beats per minute (bpm).

12.2.4. Best Corrected Visual Acuity

The BCVA will be recorded using the ETDRS chart and total number of letters at 4 meters and 1 meter will be recorded. If a subject could not read ETDRS chart, Finger Counts, Hand Motion, Light Perception, or No Light Perception will be recorded.

12.2.5. Slit-lamp Biomicroscopy

The Clinical Investigator will assess Slit-lamp biomicroscopy examination using Slit-lamp microscope. On the visit of any IVT treatment, a biomicroscopy examination will be performed prior to Lucentis® injection and a second one within 30 minutes after DE-122 or Sham injection. This will be also applied for the post IVT injection of Rescue treatment.

12.2.6. Intraocular Pressure

IOP will be measured by applanation tonometry and reported in millimeters of mercury (mmHg). On the visit of any IVT injection, IOP will be measured before Lucentis® and 40 (± 10) minutes after Lucentis® injection. If post-injection IOP is > 21 mmHg or increased ≥ 10 mmHg from pre-injection IOP, the IOP will be measured again 60 (± 10) minutes following Lucentis® injection. If there is an increase of ≥ 10 mmHg at 60 (± 10) minutes post-injection, the IOP increase of ≥ 10 mmHg will be reported as an AE.

Moreover, IOP will be measured after DE-122 or Sham injection. If post-DE-122 or Sham injection IOP is > 21 mmHg or increased ≥ 10 mmHg from pre-injection IOP, the IOP will be measured again 60 (± 10) minutes following injection. If there is an increase of ≥ 10 mmHg at 60 (± 10) minutes post-injection compared to pre-injection IOP, the IOP increase of ≥ 10 mmHg will be reported as an AE. This will be also applied for the post IVT injection of Rescue treatment.

12.2.7. Indirect Ophthalmoscopy

The Clinical Investigator will assess Indirect ophthalmoscopy using indirect ophthalmoscope. On the visit of any IVT treatment, an ophthalmoscopy examination will be performed prior to Lucentis® injection and a second one within 30 minutes after DE-122 or Sham injection. This will be also applied for the post IVT injection of Rescue treatment.

12.2.8. Urine Pregnancy Test

A urine pregnancy test will be conducted for all females of childbearing potential.

12.2.9. Serum Pregnancy Test

A serum pregnancy test will be conducted for all females of childbearing potential.

12.2.10. Serum Chemistry, Hematology and Urinalysis

Serum Chemistry, Hematology and Urinalysis will be measured by laboratory test company. The blood sample should be fasted for a minimum of 8 hours prior to blood draw for serum chemistry tests.

12.2.11. Fundus Photography

Digital color fundus photography will be taken following the procedure provided by the central reading center.

12.2.12. Fluorescein Angiography

Fundus fluorescein angiography will be taken following the procedure provided by the central reading center.

12.2.13. Adverse Events

AEs will be elicited from the subjects starting at the Screening through study exit. The information will include at least a description of the event, whether or not it is serious, onset and duration, frequency, severity, relation to masked study therapy, relation to injection procedure, location (OD, OS, OU or NA), action taken and outcome. Prior to evaluating the incidences, all AEs will be coded using the Medical Dictionary for Regulatory Activities ([MedDra, 2013](#)). Ocular and non-ocular AEs will be summarized separately. See [Section 12.1](#) for complete information regarding AE reporting.

13. PHARMACOKINETIC ASSESSMENTS

The DE-122 concentration in serum will be measured before and after Visit 1 (Day 1) and Visit 8 (Week 20) IVT administrations of DE-122 (2.0 mg and 4.0 mg) or Sham.

13.1. Serum Sample Collection

Serum samples will be collected according to the examination schedule. On days when Visit 1 (Day 1) and Visit 8 (Week 20) DE-122 IVT or Sham injections are administered, serum samples will be collected pre-Lucentis® injection and 3 hours (± 10 min) post DE-122 IVT or Sham injections. On day of the Visit 4 (Week 4) DE-122 IVT or Sham injection, serum samples will be collected prior to Lucentis® injection. See [Section 23.4.16](#) and/or separate procedure manual for the pharmacokinetic serum sample collection, storage and shipment.

13.2. Sample Analysis

Serum concentrations of DE-122 will be determined by ELISA (enzyme-linked immunosorbent assay) method at inVentiv Health Clinical, Inc.

14. OTHER ASSESSMENTS

14.1. Demographics and Baseline Characteristics

Subject demographics include age, race, sex, and ethnicity. Baseline characteristics include medical history, prior medications, and baseline results of physical examination, EKG, vital signs, BCVA, slit-lamp biomicroscopy, IOP, indirect ophthalmoscopy, SD-OCT, pregnancy test, laboratory tests (hematology, chemistry, and urinalysis), fundus photography, and fluorescein angiography. For assessments performed multiple times before the IVT injection of DE-122, the last pre-injection value will be used as the baseline value.

14.2. Immunogenicity

ADA titers will be measured in serum samples collected according to the examination schedule.

15. OTHERS

15.1. Biomarker

15.1.1. Serum Sample Collection

For the biomarker finding, serum samples will be collected according to the examination schedule and measured for levels of angiogenesis-related proteins. The serum samples will be also stored for future exploratory research to identify possible biomarkers associated with the study drug(s) and/or ophthalmologic disease conditions. See [Section 23.4.19, Appendix D](#) for procedures for the serum sample collection, storage and shipment.

15.1.2. Aqueous Humor Sample Collection

For the biomarker finding, aqueous humor samples from the study eye will be collected according examination schedule only from subjects who has consented and measured for levels of angiogenesis-related proteins. Aqueous humor samples will be also stored for future exploratory research to identify possible biomarkers associated with the study drug(s) and/or ophthalmologic disease conditions. See [Section 23.4.20, Appendix D](#) for procedures for the aqueous humor sample collection, storage and shipment.

15.2. SS-OCT Angiography

SS-OCT angiography will be taken following examination schedule at selected sites.

15.3. M-CHARTSTM

The degree of metamorphopsia will be recorded using the M-CHARTSTM, and vertical metamorphopsia score (MV) and horizontal metamorphopsia score (MH) will be recorded.

16. STATISTICAL METHODS

16.1. Analysis Time Points

One primary analysis (Week 24) and follow-up analysis (Week 32) will be performed.

16.1.1. Primary Analysis

Descriptive summaries of the following efficacy and safety measures will be provided by treatment arms at the Week 24:

- Mean change in BCVA from baseline
- Change in CST and macular volume from baseline
- Change in central retinal lesion thickness from baseline
- Proportion of subjects with BCVA Improvement of ≥ 15 letters, < 15 letters change (stable) and loss of ≥ 15 letters from baseline
- Change in total lesion area and total area of CNV from baseline
- Change in greatest linear dimension of the total lesion area from baseline
- Safety assessment include AEs, BCVA, slit lamp biomicroscopy, IOP, indirect ophthalmoscopy, serum chemistry, hematology, urinalysis, vital signs, physical examination, fundus photography, fluorescein angiography, EKG, and pregnancy

Additional variables of interest will also be provided.

16.2. General Considerations

All study parameters will be listed and a selected list of parameters will be summarized descriptively by treatment arm. The descriptive statistics will include number of observations (n), mean, standard deviation, minimum, and maximum for continuous parameter and frequency (n) and percent (%) for categorical parameters.

Details about the statistical analyses for this study will be provided in the statistical analysis plan (SAP).

All data manipulations and descriptive summaries will be implemented using SAS[®], Version 9.1.3 or later.

16.2.1. Sample Size

Approximately 76 subjects (Arm 1: 17, Arm 2: 31, Arm 3: 28) with wet AMD will be enrolled at approximately 14 sites. The final number of subjects enrolled may be adjusted based on the judgments from Safety Review Team. This sample size is not planned based on statistical considerations.

16.2.2. Statistical Hypotheses and Level of Significance

No statistical hypothesis is defined for this study.

16.2.3. Randomization

The first 6 subjects will be randomized to Arm 1 and Arm 2 in a 1:1 ratio in Stage 1. If the safety and tolerability at Week 4 are acceptable, remaining approximately 70 subjects will be randomized to all Arms in a 1:2:2 ratio in Stage 2. To balance the randomization, subjects will be stratified by subgroups on the central reading center's assessment of lesion type, up to approximately one third (1/3) of the subjects in each arm should have PCV in Stage 2.

16.2.4. Study Eye

The study eye must meet all inclusion and exclusion criteria, including confirmation by the central reading center. If both eyes are eligible based on inclusion and exclusion criteria, the study eye is defined as the eye with worse vision. If both eyes have the same vision, the right eye (OD) should be determined as the study eye.

16.3. Study Populations

The following study populations are defined for analysis: Intention-to-treat (ITT) and Safety.

ITT Population: The ITT population will include all randomized subjects in the study.

Safety Population: The Safety population will include all randomized subjects who received at least one study medication. It will be the study population for safety analyses.

PK Population: The PK population will include all subjects who received at least one DE-122 and have at least one post-injection PK assessment. It will be the study population for PK analyses performed with subjects as treated.

Full Analysis Set: The Full Analysis Set (FAS) will include all randomized subjects who received at least one study medication and provided at least one post-baseline BCVA measurement. The efficacy analysis will be performed on the FAS or a subset of the FAS.

Per-Protocol Set: The Per-Protocol Set (PPS) Population is a subset of the FAS. It includes all FAS subjects without major protocol violations that could affect the primary efficacy endpoint.

16.4. Handling of Missing Values

Primary analysis of the primary efficacy endpoint will be based on the observed cases. Missing BCVA measurements will be imputed using the Last-Observation-Carried-Forward (LOCF) approach as a sensitivity analysis. For safety measures, missing scores will not be imputed for data summaries.

Completely or partially missing onset and resolution dates for AEs and completely or partially missing start and end dates of concomitant medications will be imputed in a conservative fashion that will be detailed in the SAP.

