### **2.2. Endpoints**

#### **2.2.1. Primary Efficacy Endpoint**

The primary efficacy endpoint is mean change from baseline in Best Corrected Visual Acuity (BCVA) at Week 24.

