### 6.2. Handling of Missing Data

For safety measures, missing scores will not be imputed for data summaries.

For efficacy measures, the last-observation-carried-forward (LOCF) approach may be used to impute missing post-baseline values in sensitivity analysis. Baseline scores will not be carried forward.

Completely or partially missing onset and resolution dates of medical events, i.e., medical history events and AEs will be imputed in a conservative fashion as follows.

Date	Type of Missing Date	Handling of Missing Date
Event onset date (e.g., YYYY-MM-DD)	Completely missing	No imputation will be applied.
	Only YYYY is available	Use the first day of YYYY to impute the missing month and day of the onset date
	YYYY and MM are available but DD is missing	Use the first day of MM to impute the missing day of the onset date
Event resolution date (e.g., YYYY-MM-DD)	Completely missing	No imputation will be applied
	Only YYYY is available	Use the last day of YYYY to impute the missing month and day of the resolution date
	YYYY and MM are available but DD is missing	Use the last day of MM to impute the missing day of the resolution date

Same rules will be followed to impute completely or partially missing start and end dates of non-study medications.

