### **8.1. Primary Endpoint**

#### **8.1.1. Primary Analysis**

The primary efficacy endpoint is mean change from baseline in BCVA at Week 24. No formal statistical hypothesis testing will be implemented for the primary endpoint. Descriptive summaries will be provided by each planned treatment arm. The differences in mean change between Arm 2 or 3 and Arm 1, as well as the corresponding 95% confidence intervals based on t-test without multiplicity adjustment will also be provided. Descriptive summaries of BCVA measured at Week 28 and Week 32 will be provided, in which any records after the rescue injection(s) will be censored.

The primary analyses will be performed on the FAS. Besides the summary tables, plots of BCVA measures versus analysis visit will be provided. BCVA score, and percent change from baseline will also be summarized.

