#### **8.1.2. Sensitivity Analysis**

To assess the robustness of the primary analysis results, the same analysis may be repeated on the PPS with observed cases, and FAS with missing data imputed by the LOCF approach.

In addition, if the scheduled injection was skipped at a visit, BCVA measured at the first visit after that visit will be censored. Descriptive summaries will be performed based on the censored dataset to assess the impact of missing injection on the primary analysis results.

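### Observed-case Week 24 BCVA means are biased if dropout depends on vision, and LOCF, the only missing-data check, may err either way and is optional in the SAP

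*Protocol*

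**What the plan says.** SAP 2.2.1 defines the endpoint: "The primary efficacy endpoint is mean change from baseline in Best Corrected Visual Acuity (BCVA) at Week 24". Protocol 16.4 fixes the handling of missing values: "Primary analysis of the primary efficacy endpoint will be based on the observed cases". Protocol 16.6.1 repeats this and places the analysis on the FAS. SAP 8.1.1 gives descriptive summaries by arm, and adds the difference of each DE-122 arm from control with "95% confidence intervals based on t-test without multiplicity adjustment". SAP 6.1 rules out covariate adjustment. No hypothesis is tested; Protocol 16.2.2 states: "No statistical hypothesis is defined for this study".

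On sensitivity analysis the two documents differ in force:

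- Protocol 16.4: "Missing BCVA measurements will be imputed using the Last-Observation-Carried-Forward (LOCF) approach as a sensitivity analysis". Protocol 16.6.1 likewise commits to presenting LOCF results and to a per-protocol repeat.
- SAP 8.1.2: "the same analysis may be repeated on the PPS with observed cases, and FAS with missing data imputed by the LOCF approach". SAP 6.2 is equally permissive about LOCF, and adds: "Baseline scores will not be carried forward".

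SAP 8.1.2 has one further analysis, which drops the BCVA value at the visit after a skipped injection: "Descriptive summaries will be performed based on the censored dataset to assess the impact of missing injection on the primary analysis results". It creates missing values and does not handle any.

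**The concern.** An observed-case mean estimates the mean for everyone randomized only if those without a Week 24 value would have seen as well as those with one. LOCF is right only if the vision of those who leave would, on average, have stayed where it was last measured. Neither is a safe assumption if subjects leave because of how they see.

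BCVA is measured at seven post-baseline visits up to Week 24, yet a subject who leaves at Week 12 adds nothing to the Week 24 mean or its interval. With 17 controls, one missing control is 1/17 = 5.9% of that arm. The active arms receive a second penetrating injection and the control arm a sham that does not penetrate the eye (Protocol 9.4 and 10.7), so unequal dropout is possible.

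At stake is the plan's only between-arm inference on its primary endpoint. The SAP's permissive wording also lets the single missing-data check be run or left out after results are known.

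**Working it through.** **Inputs from the documents.** Arms of 17, 31 and 28 (Protocol 16.2.1). BCVA at Weeks 1, 4, 8, 12, 16, 20 and 24 (schedule of events). No SD, dropout rate or effect size is given.

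**The plan's own figure.** Stage 1 gives 3 + 3. Stage 2 gives 70 × (1/5, 2/5, 2/5) = 14, 28, 28. The totals are 17, 31, 28 = 76, as stated. This checks the allocation only; there is no power figure to reproduce.

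**Assumptions (not in the documents).** SD of about 10 letters. Mean change at Week 24 of +6, 0, −4 or −8. Either a random intercept plus AR(1) error, or random slopes. Once out, a subject stays out; 10–20% have left by Week 24. Poorer-seeing subjects leave, with log-odds of leaving rising by 1 per 10 letters lost. Dropout depends either on the last observed value (missing at random, MAR) or on the current unobserved value (not at random, MNAR). The repeated-measures fit has arm-by-visit means and unstructured covariance, without baseline or lesion type.

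**Step 1: direction of the bias.** With a fraction *p* missing at Week 24:

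- Observed-case bias = *p* × (Week 24 mean of stayers − Week 24 mean leavers would have had).
- LOCF bias = *p* × (mean last value of leavers − Week 24 mean leavers would have had).

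The first sign depends on who leaves. The second depends on where leavers' vision was heading. The signs are not tied together.

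**Step 2: one arm, 20% dropout, bias in letters.**

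| Trajectories and path | Dropout | Observed cases | LOCF | Repeated measures |
|---|---|---|---|---|
| Intercept + AR(1), +6 | MAR | +1.15 | −1.28 | +0.01 |
| Intercept + AR(1), flat | MAR | +1.20 | −0.72 | +0.04 |
| Random slope, −4 | MAR | +0.76 | +0.36 | −0.02 |
| Random slope, −8 | MAR | +0.81 | +0.76 | −0.02 |
| Intercept + AR(1), +6 | MNAR | +1.29 | −0.66 | +0.41 |
| Intercept + AR(1), −4 | MNAR | +1.34 | +0.35 | +0.44 |

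In the first row, 1.15/0.20 = 5.75 letters separate stayers from leavers, and leavers would have gained 1.28/0.20 = 6.4 letters after their last reading. In the −8 row leavers would have lost a further 0.76/0.20 = 3.8 letters, so both methods err upward.

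**Step 3: the arm difference, which is what SAP 8.1.1 reports.** Intercept + AR(1), MAR. The first three rows use 17/31/28 subjects, 4,000 replicates and a true difference of 0, and give Arm 2 then Arm 3, each minus Arm 1. The last three are large-sample, one active arm against control.

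| Paths | Dropout, control v active | Observed cases | LOCF | Repeated measures |
|---|---|---|---|---|
| All improving | 15% v 15% | +0.05, +0.05 | +0.08, +0.04 | +0.07, +0.05 |
| All improving | 10% v 20% | +0.60, +0.55 | −0.60, −0.63 | +0.03, −0.01 |
| All improving | 20% v 10% | −0.56, −0.48 | +0.61, +0.67 | −0.01, +0.06 |
| Control flat, active improving | 15% v 15% | −0.04 | −0.41 | −0.02 |
| Control flat, active improving | 10% v 20% | +0.53 | −0.91 | −0.03 |
| Control flat, active improving | 20% v 10% | −0.53 | +0.16 | +0.06 |

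The difference inherits the gap between arm biases: in the second row, observed cases for Arm 2, 1.14 − 0.54 = 0.60. Under MNAR with 10% v 20% dropout and all arms improving, the large-sample biases are +0.68 (observed cases), −0.29 (LOCF) and +0.26 (repeated measures).

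**Step 4: scale.** Half-width = *t* × SD × √(1/17 + 1/*n*). At SD 10:

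- Arm 2: 2.013 × 10 × √(1/17 + 1/31) = 2.013 × 3.018 = 6.07 letters.
- Arm 3: 2.017 × 10 × √(1/17 + 1/28) = 2.017 × 3.075 = 6.20 letters.

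Across SDs of 8 to 15 the range is 4.9 to 9.3. A bias of 0.6 is 0.6/6.07, about 10% of the half-width; 0.91 is about 15%.

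**The case against.** The strongest reply is that this is a descriptive Phase II study with no hypothesis and no powered sample size, for which observed-case summaries are a reasonable choice. The plan also limits missing data: the Week 24 analysis window is Days 156–183 against a visit window of 164–174 (SAP Table 3), discontinuing subjects have exit assessments where possible (Protocol 8.3), and non-completers are tabulated by reason (SAP 7.1). In the simulation the SD of the difference was about 3.2–3.3 letters for all three methods, so the model bought no precision. Unstructured covariance over seven visits has 7 × 8/2 = 28 parameters, beside 21 arm-by-visit means, in about 76 subjects.

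Much of this stands, and it limits the size of the point. Three parts do not settle it. Exit readings are mapped by study day, so an exit at Week 12 does not fill Week 24. The precision comparison used a model without baseline BCVA, so it does not speak to the adjusted model. The mismatch between protocol and SAP over LOCF does not depend on any simulation.

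Four stronger readings are tempting, and the documents do not support them:

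- *Observed cases and LOCF bracket the truth.* They can share a sign, as with declining vision above.
- *A repeated-measures model removes the bias.* That needs MAR. Under MNAR about 0.4 to 0.85 letters remained in the arm mean at 20% dropout; the upper figure comes from dropout twice as dependent on vision.
- *The sponsor expected about 5% dropout.* Protocol 7.2 only permits enrolment up to 80; it states no rate.
- *Poor responders will leave.* Protocol 8.3 does not list lack of efficacy as a withdrawal reason, so this is an assumption.

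**Conclusion.** The point holds as a modest improvement. Observed-case Week 24 means are biased if dropout depends on vision, LOCF is not a reliable check in either direction, and the SAP makes optional what the protocol promises.

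The bias in the arm difference is about 0.6 letters, at most about 0.9 in the scenarios run, when dropout or trajectories differ by arm. It is within 0.08 when they do not. Against a half-width near 6 letters this does not invalidate the plan.

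These sizes rest on an assumed SD of 10, 10–20% dropout and the assumed dropout mechanism. The difference was not simulated under stronger dependence on vision, which would raise the figures, or with the wide Week 24 window, which would lower them. The wording conflict rests on the documents alone.

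**What to change.** - **SAP 8.1.1:** estimate the Week 24 differences and 95% confidence intervals on the FAS with a repeated-measures model containing visit, arm, arm-by-visit, baseline BCVA by visit, and lesion type (PCV or non-PCV, the Stage 2 stratum). Use unstructured covariance and name the fallback in advance, such as a structured covariance with robust standard errors if the model does not converge. Keep the observed-case descriptives by arm.
- **Assumption:** state that the model is valid under MAR, and add a simple delta-adjusted analysis for dropout that depends on unobserved vision.
- **SAP 8.1.2:** change *may* to *will* for the sensitivity analyses, and align SAP 6.2.
- **Matching edits:** SAP 6.1 (covariates) and Protocol 16.4 and 16.6.1 (observed cases, descriptive statistics).

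The cost is text in both documents, one model and one sensitivity analysis; no new data are needed. The downside is reliance on MAR and on a covariance fallback in a trial of about 76 subjects.
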